Randomization:

20,000 patients will be randomized to 3 study arms related to scheduling workflow in a 1:20:20 ratio (500 usual care, 10,000 in intervention arms) to receive: 1) Phone Call (usual care), 2) Opt-In (call back), 3) Opt-in (in-bound).

- *Arm 1: Phone Call (usual care):* 500 patients will be randomized to Arm 1, Phone Call (usual care) and will receive a phone call to schedule their appointment from an Access Center representative. Access Center representatives will make up to 3 attempts to schedule an appointment with the patient. Patients randomized to this arm will not receive any text messaging.

The remaining 20,000 patients will be randomized to study arms that will receive one of 2 scheduling workflows in a 1:1 ratio (10,000 in each arm):

- *Arm 2: Opt-In (call back):* Messaging will include a prompt to agree to scheduling: "If you would like us to call you to schedule your appointment please reply, YES." The access center will call these patients back to schedule, calling up to 3 times.
- *Arm 3: Opt-in (in-bound):* Messaging will include a prompt to agree to scheduling, which will be following by a prompt to call the Penn Medicine COVID-19 Vaccine Scheduling Hotline.

Among Arms 2-3, patients will be additionally randomized to different messaging content informed by principles of behavioral science in a 1:1:1:1 ratio (2,500 in each arm):

- *Arm A: Standard messaging:* The message describes that the patient is eligible for the COVID vaccine. ("Our records show you are eligible for your COVID-19 vaccine at Penn Medicine.")
- *Arm B: Clinician endorsement:* The message will describe an endorsement from the provider to get the vaccination. ("[name] recommends that you receive the vaccination.")
- *Arm C: Scarcity:* The message will highlight the limited availability and the elevated priority for the patient to receive the vaccine at Penn Medicine. ("You have been selected to receive from the limited supply of COVID-19 vaccine at Penn Medicine.")
- *Arm D: Opt-out framing:* This will highlight that a vaccine is reserved for the patient, implying that they need to opt-out ("We have reserved a COVID-19 vaccine appointment for you at Penn Medicine.").

All study arms will be further randomized into 5 smaller batches of 500 patients each (100 in the phone

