The primary outcome will be the percentage of patients who complete the first dose of the COVID vaccine within 1 month of initial outreach. Secondary outcomes will be the completion of the first dose within 2 months, and completion of the vaccination process within 2 months of initial outreach. Additional outcomes will include the percentage of patients with invalid cell phone numbers (either wrong or non-textable numbers), non-response to text messaging, the percentage of patients that are scheduled, text message responses (YES, INFO, NOT NOW, DONE), and number of phone calls made by the access center. Heterogeneity of subgroup response through interaction analysis will be examined controlling for patient portal/email status, age, race/ethnicity, sex, insurance, and income (by zip code). We will also examine vaccine completion by vaccine type, and code and examine non-keyword replies for themes.

We estimate a 5% response rate to the phone call only. In order to minimize the outgoing phone call burden on the access center, we will include 500 patients in the outbound phone call arm (Arm 1). For the scheduling flow comparison, we will allocate 10,000 patients in each text message arm (Arms 2-3). We will compare each text message arm to the phone call arm, resulting in 2 comparisons (arm 2 vs arm 1, arm 3 vs arm 1). Accounting for 2 pairwise comparisons with a P-value threshold of .025 (Bonferroni correction; .05/2), we estimate over 85% power to detect a difference of 4 percentage points (response

rate of 9%) using the chi-squared test of proportions [STATA: power twoprop .05 .09, n1(500) n2(10000) a(.025)].

For the messaging comparison, we will allocate 2,500 patients in each arm. We will compare arms B-D to Arm A with 3 pairwise comparisons. Assuming a P-value threshold of .017 (.05/3) and a baseline response rate of 8% for text messaging, we estimate approximately 87% power to detect a difference of 2 percentage points (response rate of 10% for intervention arms) using the chi-squared test of proportions. [STATA: power twoprop .08 .10, n1(5000) n2 (5000) a(.017)]. We do not anticipate interaction between scheduling workflow and messaging arms.

Subject Confidentiality

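### Workflow comparisons: Bonferroni at .025 is valid but uses only about 3.3% familywise error against the 5% allowed, because both tests share the phone arm; Dunnett would raise power from 86% to 90%

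*Combined protocol and SAP*

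**What the plan says.** The Analysis Plan gives the primary outcome as a binary one: "The primary outcome will be the percentage of patients who complete the first dose of the COVID vaccine within 1 month of initial outreach". For the scheduling workflow it states: "We will compare each text message arm to the phone call arm, resulting in 2 comparisons", namely Arm 2 against Arm 1 and Arm 3 against Arm 1. The allocation under Procedures, Randomization is "in a 1:20:20 ratio (500 usual care, 10,000 in intervention arms" each).

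The planning assumption for the control is "We estimate a 5% response rate to the phone call only". The target is a 4-point increase, to 9%. On error control and power the plan says "Accounting for 2 pairwise comparisons with a P-value threshold of .025 (Bonferroni correction; .05/2), we estimate over 85% power", using a chi-squared test of proportions, and it prints the Stata command. It does not mention the dependence created by the shared phone arm, or any procedure other than Bonferroni.

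The phone arm is deliberately small. To spare the Access Center outgoing calls, "we will include 500 patients in the outbound phone call arm (Arm 1"). Each phone patient can generate several calls: "Access Center representatives will make up to 3 attempts to schedule an appointment with the patient".

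**The concern.** Bonferroni makes no assumption about how the tests are related. Here the relation is fixed by the design and is very strong. Both comparisons use the same 500 phone patients, and those patients supply most of the random error in each difference. If the phone arm comes out low by chance, both text arms look good together. The two tests come close to being one test, and dividing .05 by two overcorrects.

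What is at stake is power, not validity. The phone arm limits the precision of both comparisons and is capped for operational reasons, while adding text patients would hardly help. Error rate left unused in this family is therefore power that the design cannot easily obtain in another way.

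**Working it through.** **Inputs (Analysis Plan).** Phone rate 5%, text rate 9%, n1 = 500, n2 = 10,000, α = .025 per test, chi-squared test. The test is taken as two-sided, since the Stata command has no one-sided option; the one-sided calculation would give 92.4%. The Randomization paragraph opens with a total of 20,000 where other sections give 20,500, but the arm sizes used here are the same throughout.

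**1. The plan's own power figure.**
- Pooled rate = (500 × .05 + 10,000 × .09)/10,500 = .0881.
- Null SE = √[.0881 × .9119 × (1/500 + 1/10,000)] = .01299.
- Alternative SE = √[.05 × .95/500 + .09 × .91/10,000] = .01016.
- Critical value for α = .025 two-sided: 2.2414.
- Power = Φ[(.04 − 2.2414 × .01299)/.01016] = Φ(1.072) = 85.8%. This agrees with the stated figure of over 85%.

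**2. Correlation of the two tests under the null.** ρ = (1/n1)/(1/n1 + 1/n2) = n2/(n1 + n2) = 10,000/10,500 = 0.952.

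**3. Familywise error at .025 per test.** With both text arms equal to phone, the bivariate normal with ρ = 0.952 gives P(max|Z| > 2.2414) = 3.28%. Simulated three-arm binomial trials give 3.2% to 3.3% at common rates of 5%, 8% and 9%.

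**4. Dunnett threshold.** Solving P(max|Z| > c) = .05 at the same ρ gives c = 2.0686, a two-sided per-test threshold of .0386. Simulated familywise error is about 4.95% at common rates of 5% and 9%. The normal approximation therefore holds up even with only about 25 expected events in the phone arm (500 × .05).

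**5. Power at the new threshold.** Φ[(.04 − 2.0686 × .01299)/.01016] = Φ(1.293) = 90.2% (simulated 90.0%).

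| Quantity | Bonferroni .025 | Dunnett .0386 |
|---|---|---|
| Power per comparison, 5% vs 9% | 85.8% | 90.2% |
| Power per comparison, 5% vs 8% | 59.2% | 67.2% |
| Both text arms at 9%: both significant (simulated) | 83.0% | 87.7% |
| Both text arms at 9%: at least one significant (simulated) | 88.8% | 92.2% |
| Detectable difference at 80% power | 3.73 points | 3.47 points |
| Familywise error, both text arms equal to phone | 3.3% | 5.0% |

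**6. Interval width at 5% vs 9%.** The unpooled SE is 1.016 points. The phone arm contributes .05 × .95/500 = .000095 of a total variance of .0001032, so the unpooled correlation is 0.921 and the simultaneous cut-off is 2.095. The half-width is 2.095 × 1.016 = 2.13 points, against 2.2414 × 1.016 = 2.28 with Bonferroni.

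**7. Equivalent phone-arm size.** Keeping .025 and solving for n1 at 90.2% power gives 560.7, so 561 patients: 61 more than planned, each with up to 3 call attempts.

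**8. Error across both families.** The messaging family (three tests at .017) has a familywise error of about 4.54%. Treating the two families as independent, the total is 1 − (1 − .0328)(1 − .0454) = 7.7% now, and 1 − .95 × (1 − .0454) = 9.3% with Dunnett in the workflow family.

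**The case against.** The strongest reply is that nothing needs changing. Bonferroni is standard for two comparisons, holds under any dependence, and the plan already exceeds 85% power at its stated target. That is correct, and it is why this is only an optional improvement.

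A second reply is that single-step Dunnett is not the only alternative, nor always the best one. Holm uses the same p-values and needs no correlation. In simulation with both text arms at 9%, the chance that both comparisons are significant is 87.8% with Holm and 87.7% with Dunnett. With text arms at 9% and 8%, power for the 8% arm is 72% with Holm and 68% with Dunnett. Single-step Dunnett does better per comparison when both arms are at 9% (90.0% against 88.3%) and for the stronger arm when they differ (90% against 86%). Step-down Dunnett gives 91% per comparison when both are at 9%. This stands as a qualification: the choice depends on which power matters most, which the plan does not say. All of these procedures gain on fixed .025, and single-step Dunnett has the advantage of simple matching confidence intervals.

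Third, the error is unused only within this family. The plan tests one primary outcome in two families, and total error across them already exceeds 5%. That also stands, and the sponsor should weigh it. The plan's own thresholds, however, set 5% within each family, and the change stays inside that limit.

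Finally, it may be too late. The document is dated November 2021 and does not show whether outcomes by arm have been seen, so the advice has to be conditional.

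**Conclusion.** The point holds as an efficiency gain. The current plan is valid, its power statement is correct, and no conclusion under it would be biased. Bonferroni at .025 leaves familywise error at about 3.3% against the 5% allowed for the workflow family. Using the full 5% through Dunnett raises power per comparison from 85.8% to 90.2% at the planned effect, and by about 8 points at a 3-point effect.

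The result rests on the planned arm sizes, a two-sided chi-squared test and the normal approximation, which simulation supports. The 3.3% applies when neither text arm differs from phone. The power figures rest on the plan's 5% phone rate. The cross-family figures assume that the two families are independent.

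**What to change.** If no outcome data by arm have been seen, amend the SAP for the workflow family only:

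- Replace the .025 threshold with a two-sided Dunnett many-to-one adjustment: per-test threshold about .0386, |z| > 2.07.
- Report matching simultaneous 95% confidence intervals, with the cut-off taken from the estimated correlation (about 2.07 to 2.10).
- Restate power per comparison for 5% versus 9% as about 90%.
- State that each family is controlled at 5% separately and that error across the workflow and messaging families together is not controlled at 5%.
- Leave the messaging threshold as it is.

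If the sponsor cares most about showing that both text arms differ from phone, Holm or step-down Dunnett is a reasonable alternative. One procedure should be chosen and fixed in advance.

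Date the amendment before any view of outcomes by arm. If such data have been seen, keep .025 as the primary threshold. The cost is SAP wording and one restated figure, with no further patients, calls or data. The trade-off is familywise error of 5% in place of about 3.3% in this family, and about 9.3% in place of 7.7% across both.

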The COVID vaccine workgroup at Penn Medicine (including the Office of CMIO, CPUP, PMMG, Access Center, Marketing, and CHCI) has identified approximately 19,000 patients with a cell phone number who are not enrolled in MyPennMedicine (MPM) and do not have an email address in the EHR and approximately 95,000 patients who have been sent an MPM message or email and have not yet scheduled an appointment. The team has already developed and implemented a protocol to send text messages (using the Way to Health platform) to offer the vaccine and help schedule through collaboration with the Access Center. Through this program, we propose to prospectively randomize scheduling workflow and messaging to identify the most effective and equitable approaches to increasing vaccine uptake. What we propose will simultaneously [1] identify the interventions with the highest response rate that can inform Penn Medicine efforts locally and [2] conduct a pragmatic trial with a rigorous analysis plan that we can broadly apply to other contexts and share with other health systems.

Study Design

Design

This is a pragmatic randomized controlled trial with a factorial design. 20,500 patients will be included and randomized to 3 study arms related to scheduling workflow in a 1:20:20 ratio to include 500 patients in the usual care arm (phone call only) and 10,000 patients in each text messaging arm as follows: 1) Phone Call (usual care), 2) Opt-In (call back), 3) Opt-in (in-bound). Among the 20,000 patients receiving text messaging (Arms 2&3), patients will be additionally randomized in a factorial design to four different types of messaging content informed by principles of behavioral science in a 1:1:1:1 ratio (5,000 in each arm): A) Standard Messaging, B) Clinician Endorsement, C) Scarcity, and D) Opt-Out Framing.

Study duration

We anticipate 2 weeks to set up the text messaging platform, and to identify and randomize eligible patients. Phone calls and text messaging will begin at the same time, and initial outreach and all follow-up messaging will be completed within 14 days from initial outreach.

Resources necessary for human research protection

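### The only test named for the arm comparisons is unadjusted, and the baseline variables listed elsewhere in the plan enter no primary comparison: a small, avoidable loss of precision

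*Combined protocol and SAP*

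**What the plan says.** The Analysis Plan describes two families of comparisons: each text workflow against the phone call (two comparisons), and each behavioural message against standard messaging (three). For both, the test is given as "using the chi-squared test of proportions", directly followed by a Stata power command. No other sentence states how the primary outcome will be modelled.

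For workflow the inputs are "Accounting for 2 pairwise comparisons with a P-value threshold of .025 (Bonferroni correction; .05/2", "We estimate a 5% response rate to the phone call only" and "we estimate over 85% power to detect a difference of 4 percentage points". The Design section sets the allocation "in a 1:20:20 ratio to include 500 patients in the usual care arm (phone call only) and 10,000 patients in each text messaging arm".

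Baseline variables appear in the Analysis Plan only for heterogeneity of response, which is to be examined "controlling for patient portal/email status, age, race/ethnicity, sex, insurance, and income (by zip code". The Randomization text adds that "All study arms will be further randomized into 5 smaller batches of 500 patients each" (100 in the phone arm). These batches set the day of outreach, and the Analysis Plan does not mention them.

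**The concern.** By listing these variables for subgroup work, the plan treats them as relevant to response, and its Background describes lower vaccine uptake among Black patients. If they predict vaccination, a prespecified adjusted comparison would usually be more precise than the crude one without enrolling anyone. This is of most interest for the phone arm. It is capped at 500 patients to limit the Access Center's call burden, expects about 500 × 0.05 = 25 events, and anchors both workflow comparisons.

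There is also a question of prespecification. A plan that lists six covariates but writes down no primary model leaves the choice between adjusted and unadjusted results open until the data are seen.

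**Working it through.** **Inputs from the Analysis Plan.** Workflow: 5% v 9%, 500 v 10,000, alpha .025. Messaging: 8% v 10%, 5,000 v 5,000 (the power command), alpha .017. Tests are taken as two-sided. Sidedness is not stated, but two-sided reproduces the plan's figures.

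**Input assumed.** R2, the share of outcome variance explained by the covariates, is taken as 1%, 2% and 5%. The documents give no value.

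**Step 1: reproduce the stated power.** With p̄ the pooled rate, d the difference and z the two-sided critical value:

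- SE0 = √[p̄(1 − p̄)(1/n1 + 1/n2)]
- SE1 = √[p1(1 − p1)/n1 + p2(1 − p2)/n2]
- power = Φ[(d − z·SE0)/SE1]

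Workflow: p̄ = (25 + 900)/10,500 = .0881, SE0 = .01299, SE1 = .01016, z = 2.241. (.04 − .02911)/.01016 = 1.072, so power is 85.8% (plan: over 85%).

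Messaging: p̄ = .09, SE0 = .005724, SE1 = .005720, z = 2.387. (.02 − .01366)/.005720 = 1.108, so power is 86.6% (plan: about 87%).

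Both figures reproduce.

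**Step 2: apply the adjustment.** Multiply both standard errors by √(1 − R2). For messaging at R2 = 5%, SE0 = .005579 and SE1 = .005575. (.02 − .01331)/.005575 = 1.199, so power is 88.5%.

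| Assumed R2 | Workflow | Messaging, 5,000 per arm |
|---|---|---|
| 0 (crude) | 85.8% | 86.6% |
| 1% | 86.2% | 87.0% |
| 2% | 86.7% | 87.4% |
| 5% | 88.0% | 88.5% |

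The gain is 0.4 to 2.2 points for workflow and 0.4 to 1.9 for messaging. A simulation of the crude test against a stratified (Cochran-Mantel-Haenszel) test agrees in size. A covariate with a c-statistic near 0.66 added about 1 point in each comparison, and one near 0.75 added about 2. That simulation used the same covariate effect in both arms.

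**Step 3: test that assumption for workflow.** The phone arm contributes .05 × .95/500 = .0000950 to the variance of the risk difference, and a text arm contributes .09 × .91/10,000 = .0000082. The phone share is .0000950/.0001032 = 92%. In a model with common slopes, however, the slopes are estimated almost entirely from text patients. Precision improves only if those slopes also describe the phone arm.

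A check by simulation used main-effects logistic standardisation with one binary covariate at 50% prevalence (an assumption). The covariate separates text patients 5% v 13%, so it explains .04²/(.09 × .91) = 2.0% of outcome variance there.

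- No effect in the phone arm (5% v 5%): the variance of the risk difference rises by about 1%.
- A weaker effect in the phone arm (3.5% v 6.5%): it falls by less than half a percent.
- A covariate that predicts response in both arms: it falls by about 1%.

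The workflow column above is therefore an upper range.

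**Step 4: batch.** Batches are equal fifths of every arm, so batch cannot be imbalanced between arms. If rates run evenly from p(1 − h) to p(1 + h) over the five days, R2 = p²h²/2 ÷ [p(1 − p)]. At p = 8%, h = 25% gives .0002/.0736 = 0.3%, and h = 50% gives .0008/.0736 = 1.1%. In simulation, batch alone gave no gain beyond simulation error.

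**Step 5: missing covariates.** If a share m of patients is dropped for missing data, the effective sample size is n(1 − m)/(1 − R2). Once m exceeds R2 the gain is gone.

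**The case against.** The strongest reply is that nothing here is an error. A crude comparison of randomised arms is valid, and chance imbalance, including in the 500-patient arm, is already allowed for in the test's error rate. That stands.

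The chi-squared test appears only in the power statements. A reader might infer that the plan has fixed it as the primary analysis, but powering on a crude test does not settle the analysis model. What can be said is that it is the only test named and that no adjusted comparison is planned.

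A reader might also infer that adjustment would shrink the standard error of every arm contrast. Step 3 shows that this is not assured for workflow. Nor do the documents support treating batch as a source of power: it is balanced by design, it was created to spread call volume, and its contribution is close to nil.

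The change is also not quite costless. The documents name the covariates but do not say they are complete, and a complete-case model could lose more than it gains.

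The case for prespecified adjustment survives these points, as a minor improvement.

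**Conclusion.** The point holds as a minor loss of precision, with no effect on validity. For messaging, at an assumed R2 of 1% to 5%, power would rise from 86.6% to between 87.0% and 88.5%. For workflow the ceiling is 86.2% to 88.0% against 85.8%, and the gain may be nil if the covariates act differently in the phone and text arms. No sample size or error rate changes. Writing down one primary model is worth as much as the added power.

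The messaging figures assume 5,000 per arm, as in the Design section and the power command. The Randomization text and the Analysis Plan prose say 2,500, which is the size of one workflow-by-message cell (20,000/8). At 2,500 per arm the crude power is 53.4%. That conflict is a separate matter and far larger than this one, and the passages must be reconciled.

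**What to change.** Prespecify as the primary analysis a logistic model on all randomised patients with arm terms and the listed covariates: portal/email status, age, race/ethnicity, sex, insurance and zip-code income. State how each is coded. Message terms apply to text patients only, since the phone arm receives no messages. Keep patients with missing covariates in the model through a missing category or simple imputation. Report standardised risk differences with robust standard errors, so that the result is still a difference in the percentage vaccinated. Retain the chi-squared test as the unadjusted sensitivity analysis. Batch may be included because it is part of the randomisation, but it should not be presented as a source of power.

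The cost is a paragraph in the plan, a little more analysis work and a rule for missing covariates. No additional patients are needed, and the covariates are ones the plan already intends to analyse.
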